7 STUDY PROCEDURES

Before the start of the study, subjects must read and sign the current version of informed consent form (ICF) approved by the Ethics Committee (EC). All examinations and study procedures will be carried out according to the schedule of activities, and will not be affected by the duration of drug interruption. However, it is allowed to change within the window period of test items due to holidays, weekends or other administrative reasons.

7.1 Screening Period (D-21 to D-1)

Unless otherwise stated, the following screening procedures must be completed within 21 days prior to the first dose:

[Signing of ICF] A written ICF must be signed by the subject before any procedures of the clinical study are carried out.

[Demographics] gender, date of birth, ethnicity, height, weight, smoking history.

[Tumor history] including pathological diagnosis and clinical diagnosis:

- (1) Tumor diagnosis: the date of initial diagnosis of the tumor, histological classification, site of primary tumor and metastatic lesions, pathological staging, and clinical staging;
- (2) History of surgery: the surgical history of primary lesions and the surgical history of metastatic lesions;
- (3) History of chemotherapy (including new/adjuvant chemotherapy): the history of systemic chemotherapy, the history of targeted drug therapy, and the history of local chemotherapy;
- (4) History of radiotherapy: date, dose, and site (systemic/local);
- (5) Results of gene mutation detection (if applicable): whether there are gene mutations, sites of mutation, and detection date;
- (6) The date of PD or disease recurrence after the last systemic treatment.

[Concomitant disease] Concomitant disease and related treatment history (such as diabetes, hypertension and other chronic diseases), history of tumors other than non-small cell lung cancer.

[Concomitant medication] Concomitant medications and treatments received within 30 days prior to the first dose and during the study period should be recorded. Once the study treatment is interrupted, only the concomitant medication and treatment used to solve new or unresolved treatment-related AEs will be recorded;

[Thyroid function] Including serum FT3, FT4, and TSH;

[Examination of the pituitary adrenal axis] Including ACTH and cortisol.

[Hepatitis B, hepatitis C, and HIV examinations] hepatitis B panel (If the test results are abnormal, viral replication [HBV DNA] test should be performed); hepatitis C virus antibody (anti-HCV) test (If the test results are abnormal, virus titer should be tested); HIV antibody test.

[Detection of EGFR mutations and ALK fusion gene] If the subjects have previously been tested for EGFR mutations and the ALK fusion gene, they do not need to be tested again. If the subjects have not been tested previously, the study site will carry out relevant tests. If the subjects are positive for EGFR mutations, the test of ALK fusion gene will no longer be performed.

[Adverse events] Adverse events will be recorded from the time when the subjects sign the informed consent form. AEs unrelated to the study drugs will be recorded to 30 days after the last dose. Treatment-related AEs will be collected until 90 days after the last dose of SHR-1210 or 30 days after the last dose of targeted anti-angiogenic therapy (whichever is longer). See the AE/SAE collection time limit in Section 8.3 for details.

[Blood pressure monitoring] The blood pressure measurement of subjects will be performed by the investigator during the screening period; during each blood pressure measurement, smoking and coffee are prohibited within 30 min before the measurement, and subjects should rest for at least 10 min. The sitting position will be taken during the measurement by placing the elbow at the same level as the heart. Each blood pressure measurement will be taken on the same side of the body;

[Pulmonary function test] Maximum vital capacity, the forced expiratory flow at 25-75% of forced vital capacity (FEF25-75), the peak expiratory flow (PEF), maximum expiratory volume per second, diffusing capacity of the lungs for carbon monoxide (DLCO) and oxygen saturation. Carried out during the screening period and then according to the judgment of the investigator in subsequent cycles;

[Imaging examination] Including CT or MRI of the chest, abdomen, and brain. The baseline tumor assessment during the screening period can be extended to up to 3 weeks before treatment. Qualified CT/MRI scan results obtained before signing the informed consent can be used for tumor assessment during the screening period. Bone scan should be performed upon clinically suspected bone metastasis. Absence of cerebral hemorrhage should be confirmed within 21 days before randomization for subjects with stable brain metastases;

[Biomarker sampling/sample collection and detection] Archived paraffin-embedded tumor samples or fresh biopsy specimens will be collected to make ≥ 10 slices, of which 3-5 slices of 3-4 μm tumor sections (mounted slides) will be collected for the histochemistry detection of biomarkers such as PD-L1, and 5-8 slices of 5-8 μm paraffin sections (paraffin rolls can be directly collected without being mounted on the slides) or fresh biopsy specimens will be collected for the detection of biomarkers such as tumor mutation burden (TMB). Refer to the laboratory manual for details on tumor tissue sampling/sample collection and disposal methods.

For cohort 4, the test results of tumor mutation burden (TMB) in the peripheral blood and/or tumor tissues will be verified before the subjects take the first dose of the study drug, so the TMB test for cohort 4 must be completed before the first dose. However, the delay in the screening period caused by TMB testing is allowed, but other tests (including imaging examinations) must be completed within 21 days prior to the first dose.

Unless otherwise stated, the following screening procedures must be completed within 7 days prior to the first dose:

[Hematology] White blood cell count (WBC), absolute neutrophil count (ANC), lymphocyte count (LYM), red blood cell count (RBC), hemoglobin (Hb), and platelet count (PLT);

[Urinalysis] Urine protein (Note: if urine protein $\geq 2+$, 24-h urine protein quantification test shall be performed), urinary red blood cells, urinary white blood cells, and urine glucose;

[Routine stool test] Occult blood; re-examination is required for fecal occult blood+; if fecal occult blood is confirmed, then a gastroscopy shall be performed. Performed within 7 days before enrollment, on Day 15 of Cycle 1 and Day 1 of subsequent cycles, and upon completion of the study;

[Blood biochemistry] bilirubin total, bilirubin conjugated, ALT, AST, AKP, γ -GT, protein total, albumin, urea or urea nitrogen, creatinine, uric acid, fasting blood glucose, TG, cholesterol, potassium, sodium, chlorine, calcium, phosphorus, blood lipase (only checked in the screening period and in the case of subsequent abdominal pain, abdominal distension and other symptoms of suspected pancreatitis), blood amylase (only checked in the screening period and subsequent abdominal pain, abdominal distension and other symptoms of suspected pancreatitis);

[Coagulation function] Including INR, APTT, PT, TT, and FIB;

[Myocardial zymography]

[Pregnancy test] The urine pregnancy test shall be performed 72 h before the first dose in women of childbearing age. If positive, a serum pregnancy test shall be performed. If necessary, a re-test can be performed for confirmation;

[Vital signs] Body temperature, heart rate, respiratory rate, and blood pressure;

[Physical examinations] General conditions, head and face, skin, lymph nodes, eyes (sclera, pupil), ear, nose, throat, respiratory system, cardiovascular system, abdomen (including liver and spleen), reproductive-urinary system, musculoskeletal system, nervous system, and mental status;

[ECOG PS] See Appendix II;

[12-Lead ECG] Two additional ECGs or other investigations may be added as determined by the investigator if results are abnormal;

[Echocardiography]

[Blood sampling for tumor markers] In the baseline period (before drug administration), 14 mL of blood samples will be collected and divided into two tubes, with 10 mL in one tube and 4 mL in the other tube. See the laboratory manual for methods of blood sampling and disposal.

The inclusion and exclusion criteria will be verified again. Subjects must meet all inclusion criteria and must not meet any of the exclusion criteria before they can be included in the study.

7.2 Treatment Period

- Stage I study (except for subjects participating in the expanded PK study) and Stage II study
D1 of Cycle 1 [Vital signs] [Physical examinations and weight measurement] [Intravenous drip of SHR-1210] [Dispensation of apatinib] [Administration of apatinib]

Within 24 h after the first dose, the patients should be closely monitored for acute allergic reactions. If an acute allergic reaction occurs, it should be treated according to the medical practice of the hospital and relevant guidelines.

Apatinib is administered continuously from D1 of Cycle 1, and its dose can be interrupted or modified according to the occurrence of adverse events.

D1 of subsequent cycles [Hematology] [Blood biochemistry] [Urinalysis] [Routine stool test] [Coagulation function] [Vital signs] [Physical examinations and weight measurement] [ECOG PS] [ECG] [Intravenous drip of SHR-1210] [Adverse events] [Concomitant medication] [Return/dispensation of apatinib]

D15 of Cycle 1: [Hematology] [Blood biochemistry] [Urinalysis] [Routine stool test] [Coagulation function] [Vital signs] [Physical examinations] [ECG] [Intravenous drip of SHR-1210] [Adverse events] [Concomitant medication]

D15 of subsequent cycles: [Hematology] [Blood biochemistry] [Urinalysis] [Coagulation function] [Vital signs] [Physical examinations] [ECG] [Intravenous drip of SHR-1210] [Adverse events] [Concomitant medication]

A window period of ± 3 d is set and the administration of SHR-1210 should be carried out after completing the evaluation of examinations and tests specified in the flowchart.

- Subjects participating in the expanded PK study

D1 of Cycle 1: [Vital signs] [Physical examinations and weight measurement] [Intravenous drip of SHR-1210] [PK blood sampling]

D15 of Cycle 1: [PK blood sampling] [Hematology] [Blood biochemistry] [Urinalysis] [Routine stool test] [Coagulation function] [Vital signs] [Physical examinations] [ECG] [Adverse events] [Concomitant medication]

After the blood sampling on D22 of Cycle 1 is completed, continuous oral administration of apatinib will be started at a frequency of once a day.

PK blood sampling will be carried out on D28 of Cycle 1 after the administration of apatinib.

D1 of Cycle 2: [Hematology] [Blood biochemistry] [Urinalysis] [Routine stool test] [Coagulation function] [Vital signs] [Physical examinations and weight measurement] [ECOG PS] [ECG] [Adverse events] [Concomitant medication] [Return/dispensation of apatinib] [Intravenous drip of SHR-1210] [PK blood sampling]

D15 of Cycle 2 and subsequent cycles: [Hematology] [Blood biochemistry] [Urinalysis] [Coagulation function] [Vital signs] [Physical examinations] [ECG] [Intravenous drip of SHR-1210] [Adverse events] [Concomitant medication]

PK blood sampling will be carried out on D28 of Cycle 2 after the administration of apatinib.

See the flow chart and "3.3.2 Blood Sample Processing and Testing" for the time points, volume, and processing of blood sampling.

D1 of subsequent cycles [Hematology] [Blood biochemistry] [Urinalysis] [Routine stool test] [Coagulation function] [Vital signs] [Physical examinations and weight measurement] [ECOG PS] [ECG] [Intravenous drip of SHR-1210] [Adverse events] [Concomitant medication] [Return/dispensation of apatinib]

[Imaging evaluation] During the treatment period, imaging examinations should be performed under the same conditions as those at baseline (layer thickness of the scan, use of contrast agent, etc.), and the lesions found at baseline should be checked every 2 cycles in the first 6 cycles of the treatment (bone scan shall be performed in the case of suspected bone progression or for CR confirmation). After 6 cycles, imaging examinations can be performed every 3 weeks as appropriate and can be performed upon the discovery of suspected new lesions. Initial assessment of PR/CR must be confirmed after 4 weeks; initial assessment of PD must be confirmed after 4 to 6 weeks (except for significant changes in the subjects' symptoms or rapid tumor progression).

[Thyroid function test] Performed on Day 1 of Cycle 2 and then once every 3 cycles.

[Biomarker collection] For subjects showing CR/PR during the study, an additional collection of 1 tube of 10 mL blood sample for biomarker detection should be performed upon the onset of CR/PR and PD, respectively. The collection requirements are the same as those in the baseline period.

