6.3 Administration Regimen

SHR-1210 will be administered via intravenous drip (without prophylaxis) with a fixed dose of 200 mg within 30 min (not less than 20 min, no more than 60 min), once every 2 weeks. Each cycle contains 4 weeks (the subjects for the expanded PK study will receive one dose on D1 of Cycle 1 of the study) and the longest period of drug use is 2 years.

Apatinib will be orally administered after meals (the subjects for the expanded PK study will receive the drug orally under fasting on Day 28 of Cycle 1 and Day 28 of Cycle 2), once a day, and one tablet (250 mg/tablet or 375mg/tablet) or 2 tablets (250 mg/tablet, 500 mg dose group) each time. The drug administration will be continued through the study.

Subjects enrolled for the study in the tolerability observation stage and subjects enrolled for the Stage II of the study will be given SHR-1210 on D1 and D15 of each cycle from the beginning of treatment; apatinib will be given via oral administration once daily.

Subjects enrolled for the expanded PK study will be given SHR-1210 on D1 in Cycle 1 and on D1 and D15 in each cycle starting from Cycle 2. These subjects will also be given daily oral administration of apatinib continuously starting from D22 in Cycle 1.

Definition of postprandial administration: administration within 30 min after the end of a meal.

The subjects will continue to use the study drugs until the criteria for treatment discontinuation specified in the protocol are met.

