2.1. Study Design

Study design of Stage I:

A multi-arm, multi-center, open-label clinical study

Patients with advanced NSCLC who have failed standard treatment will be enrolled.

Three dose groups, i.e., apatinib 250 mg, oral, q.d. + SHR-1210 200 mg, IV, q2W, apatinib 375 mg, oral, q.d. + SHR-1210 200 mg, IV, q2W, and apatinib 500 mg, oral, q.d. + SHR-1210 200 mg, IV, q2W, are set to explore the tolerability of the combination therapy.

Ten to twelve subjects will be enrolled in each dose group (to make sure that at least 10 subjects will complete the tolerability evaluation), and the first cycle (28 days) of continuous treatment will be used as the observation period for tolerability. A dose will be considered tolerable if the proportion of subjects with clinically significant toxicity is < 0.33 .

After completing the tolerability observation period, subjects will continue the treatment until occurrence of any event that meets the criteria for discontinuation.

After completing the tolerability observation period, the study will enter Stage II for further observation of efficacy and safety.

After completing the tolerability observation period, 10 to 12 subjects will be enrolled in each dose group for an expanded pharmacokinetic (PK) study. In cycle 1 of the expanded PK study, one dose of SHR-1210 will be administered on D1 followed by PK blood sampling. Then, apatinib will be started on D22 after the completion of PK blood sampling, while another PK blood sampling will be carried out on D28. Starting from D1 of cycle 2, SHR-1210 will be administered once every 14 days, while apatinib will be administered orally every day. PK blood sampling will be carried out on D1 of cycle 2 after the administration of SHR-1210 and on D28 after the administration of apatinib. After the blood sampling is completed, subjects will continue the treatment until occurrence of any event that meets the criteria for discontinuation.

Design of Stage II:

A single-arm/double-arm, multi-center, open-label clinical study

According to the tolerable doses for combination therapy determined in Stage I, apatinib 250 mg, q.d. oral + SHR-1210 200 mg, IV, q2W are selected, and patients with advanced NSCLC who have failed first-line chemotherapy or patients with non-squamous non-small cell lung cancer with a high tumor mutation burden (TMB) confirmed by the central laboratory will be enrolled. According to the molecular and pathological classifications, the subjects are divided into:

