5. STATISTICAL ANALYSIS

All efficacy and safety analyses will be based on the following populations/groups:

- **Driver gene negative population:** Subjects who are negative or not tested for EGFR and also negative or not tested for ALK fusion gene are classified into negative population. Including:
 - (1) Apatinib 250 mg + SHR1210 200 mg (Stage I): subjects who are negative or not tested for EGFR and also negative or not tested for ALK fusion gene;
 - (2) Cohort 1;
 - (3) Cohort 3;

Apatinib 250 mg + SHR1210 200 mg are used in both Cohorts 1 and 3 in Stage II.

- **Driver gene positive population:** Subjects who are positive for EGFR or ALK fusion gene are classified into positive population. Including:
 - Subjects who use apatinib 250 mg + SHR1210 200 mg and are positive for EGFR or ALK fusion gene in Stage I;
 - Cohort 2: Apatinib 250 mg + SHR1210 200 mg are used in Cohort 2.
- **Cohort 4:** Apatinib 250 mg + SHR1210 200 mg are used in Cohort 4.
- **Apatinib 375 mg + SHR1210 200 mg:** Only subjects who receive apatinib 375 mg + SHR1210 200 mg in Stage I are included.

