5.1. General Considerations

5.1.1. Analysis sets

Full analysis set (FAS)

All enrolled subjects who have received at least one dose of the study drug are included.

Evaluable analysis set (ES)

ES is a subset of FAS, which is defined as the subjects who have received at least one dose of the study drug, and have at least one post-baseline imaging response evaluation. If there is a new anti-tumor treatment, there should be a post-baseline tumor imaging response evaluation no later than the start date of the new anti-tumor treatment.

Per-protocol set (PPS)

All enrolled subjects who have received at least one dose of the study drug without major protocol deviation.

Safety set (SS)

All enrolled subjects who have received at least one dose of the study drug.

DLT analysis set

Subjects enrolled in Stage I who have developed DLT during the tolerability observation period (four weeks) or have completed the tolerability observation period. Subjects with SHR-1210 dose < 90% of the prescribed dose due to non-clinically significant toxicity (such as injection reaction) during the tolerability observation period are not included in the DLT analysis set.

Table 1. Analysis sets and corresponding endpoints

Endpoint	Analysis Sets				
	FAS	ES	PPS	SS	DLT Analysis Set
BOR (%)	X	X	X		
ORR (%)	X	X	X		
CBR (%)	X	X	X		
TTR (months)	X				
PFS (months)	X				
DoR (months)	X				
12-Month Overall Survival Rate (%)	X				
OS (months)	X				
Safety (AE, LAB, VS, ECG, and PE)				X	
DLT Events					X

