5.3.6. Progression-free survival (PFS)

PFS is defined in Section 4.1.6.

According to population/cohort, the Kaplan-Meier method will be used to analyze the median PFS, the corresponding 95% CI will be calculated using the Brookmeyer-Crowley method, and the PFS plot will be drawn. The proportion of subjects with PFS greater than or equal to 6/9/12 months will also be analyzed. The Kaplan-Meier method will be used to analyze the 6-, 9-, and 12-month PFS rates, and the corresponding two-sided 95% CIs will be calculated (using the log(-log) transformation by normal approximation with back transformation).

The K-M curve of PFS of apatinib 250 mg + SHR1210 200 mg (Stage I) vs. apatinib 375 mg + SHR1210 200 mg will be plotted.

5.3.7. 12-month overall survival rate (12-OS%)

12-OS% is defined in Section 4.1.7.

The Kaplan-Meier method will be used to analyze the 12-OS% of each population/cohort, and the corresponding two-sided 95% CI will be calculated (using the log(-log) transformation by normal approximation with back transformation).

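### Stage I results by apatinib dose, and the pooled driver-gene results, mix subjects who start both drugs on Day 1 with PK-expansion subjects who start apatinib on Day 22; show the two separately

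*Protocol*

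**What the plan says.** **Two start schedules.** For the PK expansion, Protocol 6.3 says "Subjects enrolled for the expanded PK study will be given SHR-1210 on D1 in Cycle 1 and on D1 and D15 in each cycle", the twice-per-cycle part applying from Cycle 2, and "These subjects will also be given daily oral administration of apatinib continuously starting from D22 in Cycle 1". Protocol 7.2 agrees: "After the blood sampling on D22 of Cycle 1 is completed, continuous oral administration of apatinib will be started". For all other subjects (Stage I tolerability and Stage II), Protocol 7.2 says "Apatinib is administered continuously from D1 of Cycle 1", and Protocol 6.3 gives SHR-1210 on Days 1 and 15 of every cycle. SAP 2.1 repeats the delayed schedule and its size: "10 to 12 subjects will be enrolled in each dose group for an expanded pharmacokinetic (PK) study".

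**One analysis label.** SAP 5 defines groups by Stage I dose. The driver-negative pool takes in "Apatinib 250 mg + SHR1210 200 mg (Stage I): subjects who are negative or not tested for EGFR" and likewise negative or untested for ALK, together with Cohorts 1 and 3. The driver-positive pool adds Stage I 250 mg positives to Cohort 2. The 375 mg group is Stage I only. For the full analysis set (FAS), SAP 5.1.1 says: "All enrolled subjects who have received at least one dose of the study drug are included". The safety set has the same one-dose threshold. PFS and OS start at first dose (SAP 4.1.6, 4.1.8), and treatment-emergent events start at first study treatment (SAP 4.2.1).

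**The dose display.** SAP 5.3.6 plans "The K-M curve of PFS of apatinib 250 mg + SHR1210 200 mg (Stage I) vs. apatinib 375 mg" + SHR-1210, SAP 5.3.8 plans the same for OS, and SAP 5.4.3 summarises adverse events by apatinib dose.

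**The concern.** The SAP describes the delayed schedule in its design section and does not use it again. It has no flag, exclusion or sensitivity analysis for it; only the PK analysis itself goes to a separate report. That expansion subjects enter the dose groups is an inference, since SAP 5 never names them. But the expansion belongs to Stage I, one dose is enough for the FAS and safety set, and nothing leaves these subjects out.

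A reader of the 250 v 375 mg curves will take them to show two doses of a combination given from Day 1. If the delayed-start share differs between the doses, part of any gap between the curves could be a schedule effect. The dose-group adverse event table would also count events from Days 1-21 under an apatinib dose that had not yet been taken.

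**Working it through.** **Check of the schedule.** The protocol counts 35 PK sampling points. Cycle 1 Day 1 to Day 22 around SHR-1210 gives 9, Cycle 1 Day 28 gives 9, Cycle 2 Day 1 to Day 15 gives 8, and Cycle 2 Day 28 gives 9: 9 + 9 + 8 + 9 = 35. The stated count is reproduced, so the schedule with apatinib starting after the Day 22 sample is internally consistent.

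**Exposure by the first scheduled scan (week 8, Day 56; Protocol 10).**

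| | Both drugs from Day 1 | PK expansion |
|---|---|---|
| Apatinib days to Day 28 | 28 | 28 - 21 = 7 |
| Apatinib days to Day 56 | 56 | 56 - 21 = 35 |
| SHR-1210 doses to Day 28 | 2 | 1 |
| SHR-1210 doses to Day 56 | 4 | 1 + 2 = 3 |

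The lead-in is 21/30.4375 = 0.69 months of PFS and OS time.

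**Share of a Stage I dose group.** With 10-12 tolerability and 10-12 PK subjects per dose (SAP 2.1), the share runs from 10/(10 + 12) = 45% to 12/(12 + 10) = 55%. Protocol 3.1.2 lets the tolerability part stop once at least 7 subjects are free of clinically significant toxicity. With 7 tolerability subjects the share is 12/(12 + 7) = 63%.

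**Share of the pools.** Planned cohort sizes are 78 (Cohort 1), 38 (Cohort 2) and 38 (Cohort 3). The documents do not give the driver status of Stage I subjects, so each share runs from 0 to a maximum reached if all Stage I 250 mg subjects had that status. With 12 + 12 such subjects:

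- Driver-negative: 12/(24 + 78 + 38) = 12/140 = 8.6%.
- Driver-negative, non-squamous version: 12/(24 + 78) = 12/102 = 11.8%.
- Driver-positive: 12/(24 + 38) = 12/62 = 19.4%.

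With 12 PK and 10 tolerability subjects these become 12/138 = 8.7%, 12/100 = 12.0% and 12/60 = 20.0%.

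**SHR-1210 intensity under SAP Table 3.** The table plans a dose every 14 days for everyone. Take a fully compliant expansion subject after two cycles. The last dose is on study Day 43, so the planned duration is 43 - 1 + 14 = 56 days, or 56/14 = 4 planned doses. Three were given, and 3/4 = 75%. This falls in the below-80% category of SAP 5.4.1 although no scheduled dose was missed. After three cycles the figure is 5/6 = 83.3%, and after six it is 11/12 = 91.7%.

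**Are equal shares secured?** Protocol 3.1 opens the expansion only for a dose confirmed as tolerable. The synopsis, Protocol 3.2.1 and 4.1, and SAP 2.1 speak of each group. Protocol 3.2.1 also replaces subjects who do not complete PK sampling, so more than 12 may be enrolled at a dose while the non-completers stay in the FAS. Equal shares are therefore the simplest reading of the plan, but nothing guarantees them.

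**The case against.** The case for leaving the SAP alone has several good parts.

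- **Little rests on these comparisons.** SAP 3 plans no hypothesis and no inference, the 250 v 375 mg items are plotted curves, and the Stage II dose had already been chosen from the tolerability observation. This stands and limits the weight of the point.
- **Efficacy is also presented by cohort.** Every Stage II subject starts both drugs on Day 1, so Cohorts 1-4 reported alone contain no delayed-start subjects. This stands.
- **The prior-line subgroup in SAP 5.3.11 already helps.** It largely separates Stage I from Stage II in the driver-negative pool. It does not separate the two parts of Stage I, so the mixing in the dose curves remains.

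Three stronger readings are tempting, and the documents do not support them.

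- A reader might infer that the 375 mg group had no expansion, because the SAP has no 500 mg group and Protocol 3.1 makes expansion conditional. That is possible, but no section says so.
- A reader might infer that progression during the first 21 days is credited to the combination on a large scale. PFS runs to documented progression and the first scheduled scan is at week 8. Apart from deaths and unscheduled scans, nothing is observed in that window. Treating SHR-1210 alone as inactive is also unsupported: Protocol 1.7.1 reports disease control in 5 of 11 NSCLC subjects on it.
- A reader might infer that someone who leaves before Day 22 is counted as treated with the combination. Such a subject is in the FAS and safety set, but SAP 5 words the 375 mg and driver-positive groups by receipt or use of the drugs. Placement is unclear, not settled.

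**Conclusion.** The point holds as a cheap improvement to descriptive output. Followed as written, the SAP puts two start schedules under one combination label in the Stage I dose curves, the pooled driver-gene results and the adverse event summary by dose. In each expanded Stage I dose group about half the subjects are affected by plan. In the pools the dilution is small on the driver-negative side and could reach about a fifth on the driver-positive side, both under the extreme assumption that all Stage I 250 mg subjects share one driver status. If SAP 5.4.3 counts Stage II subjects in its 250 mg column, the share there is only 10/(20 + 174) = 5.2% to 12/(24 + 174) = 6.1%.

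If both doses were expanded in equal proportion, the 250 v 375 mg curves are not differentially biased, though neither describes the combination from Day 1. If the proportions differ, dose and schedule are confounded and the planned display cannot show it. The documents allow either case. The size of any effect on PFS or ORR cannot be derived from them. The Table 3 result needs no efficacy assumption.

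**What to change.** These are changes to SAP wording and programming only; no dosing rule is touched.

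1. In SAP 5, flag PK-expansion subjects within each Stage I dose group.
2. In SAP 5.3.6 and 5.3.8, draw the 250 v 375 mg PFS and OS curves separately for tolerability and PK-expansion subjects, and state how many of each there are per dose.
3. Report pooled driver-gene ORR and PFS with and without PK-expansion subjects, keeping the pooled result.
4. In the adverse event summary by apatinib dose (SAP 5.4.3), flag events before the first apatinib dose. List and footnote subjects who never took apatinib, and state which column holds them. Do not remove them: that would condition on a post-baseline event and drop early deaths and withdrawals.
5. In SAP Table 3, base planned SHR-1210 doses for these subjects on their own protocol schedule, so that full compliance at two cycles does not read as 75%.

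The cost is precision: each Stage I curve would rest on about 10-12 subjects. That is acceptable because the comparison is descriptive and the pooled result is kept.
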